8. RESEARCH QUESTION AND OBJECTIVES

Treatment satisfaction in COPD is associated with disease knowledge: subjects who claim to be more informed are more satisfied with their management. Long-term data on the patients' satisfaction to COPD medical treatments (i.e. pharmacological and not pharmacological treatment) in Italy are scarce. Further, there is limited information on the relation between satisfaction and clinical and patients' parameters. The present study will explore the patients' satisfaction to COPD medical treatment in a clinical real- world setting and how this is related to clinical parameters, quality of life, illness perception and treatment adherence evolution during 12-month follow up.

The patients will be also described as far as health status, presence of dyspnea, exacerbation occurrence, patient disease perception and awareness and adherence to COPD treatment during a 12-month follow up. Finally, health care resources utilization and related cost according to the Italian National Health Service during 12-month observation will be estimated and the correlation between patients' satisfaction and resource utilization will be assessed.

Primary Objective

To describe the patients' satisfaction to COPD medical treatments (by means of the TSQM9) during a 12-month observation period (namely, at enrolment, and after 6 and 12 months) in real- world setting.

Secondary Objectives

5. To describe patient disease perception (by means of illness perception questionnaire B-IPQ), adherence to COPD treatment (by means of MMAS4), health status (by means of CAT questionnaire) and dyspnea (by means of MMRC) during a 12-month observation period.
6. To analyze the relation between treatment satisfaction and demographic (such as age, gender), clinical (such as number of exacerbations, spirometric parameters) parameters and PROs during a 12-month observation period.
7. To describe the health care resources utilization and related cost according to the Italian National Health Service (INHS) during a 12-month observation period.
8. To assess the correlation between patients' satisfaction and resource utilization.

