The patients switching treatment during observation period will not be excluded from analysis and will be evaluated at each visit as above described. Few patients are expected to stop treatment during study; if any, for primary objective evaluation they will be censored at the latest available visit. Comparisons of satisfaction between different treatment/devices are not matter of this study, throughout all analysis treatments will be lumped together.

Secondary objectives

#1 To describe patient disease perception (B-IPQ), adherence to COPD treatment (MMAS4), health status (CAT) and dyspnea (MMRC) during a 12-month observation period

A description of B-IPQ (consequences, timeline, personal control, treatment control, identity, concern, emotions and illness comprehensibility), MMAS-4, CAT and MMRC scores will be provided at baseline and at follow-up visits. Scale scores will be summarized at each time point. Patients lost to follow up will be considered until their last available visit. Missing items of questionnaires/scales will be replaced if applicable according to scoring algorithm [32-38].

#2 To analyse the relation between treatment satisfaction for medical treatment and demographic/clinical parameters and PROs during a 12-month observation period

Three regression models (one for each TSQM-9 domain score) will be estimated; the dependent variable will be domain score and the independent ones will be: age and gender (at enrollment), number of exacerbations, relevant spirometry parameters (such as FEV1, FVC, FEV1 % of the predicted, RV, TLC, DLCO), level of dyspnea (MMRC score), impact of COPD on a patient's life (CAT) and treatment adherence (MMAS-4 score) collected during observational period. Because dependent variable will be collected at each study visit, repeated measures models will be estimated taking into account all available values for dependent and independent variables. Patients could be classified in mild or moderate/severe according to lung function parameters. This will allow to evaluate treatment satisfaction in different groups of patients.

The patients switching treatment during observation period will not be excluded from analysis and will be evaluated at each visit. The patients stopping treatment during study will be censored at last available visit.

#3 To describe the health care resources utilization and related cost during a 12-month observation period

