Table 17. Relation between treatment satisfaction and demographic/clinical parameters and PROs during 12 month observation period (Repeated measures regression models) – Effectiveness domain

A regression model will be estimated; the dependent variable will be the effectiveness domain score of TSQM-9 and the independent ones will be the following:

- age and gender at enrollment;
- number of exacerbations at enrollment;
- relevant spirometry parameters at enrollment (a selection of the following parameter will be done, based on data availability: FEV1, FVC, FEV1 % of the predicted, RV, TLC, DLCO);
- patient's disease severity in terms of level of dyspnea (mMRC score) or CAT total score (depending on data availability) at enrollment (since they are expected to be intercorrelated measures, as reported by 2017 GOLD guidelines, only one of such measures will be considered in the model);
- MMAS-4 score at enrollment.

Center will be included as random effect and study visit (visit1/enrollment, visit2/6months, and visit3/12months) as timepoint.

During data elaboration, the Biostatistician will assess the intercorrelation between the proposed variables, in order to evaluate the opportunity to exclude some of the listed independent variables that are highly associated to each other; in case of important lack of data for certain parameters, such parameters may be excluded as well from the final model.

Because measures referred to the dependent variable will be collected at each study visit, a mixed model for repeated measures will be estimated; moreover, interaction terms between independent variables will be evaluated and, if not significant, they will not be included in the final model. The optimal covariance structure will be evaluated during analysis (preferably "first-order autoregressive correlation" or "unstructured" options). A stepwise selection method will be evaluated during the analysis in order to identify the variables to be included in the final model.

The patients switching treatment during observation period will not be excluded from analysis. The patients stopping treatment during study will be censored at last available visit.

The analysis will be performed considering only evaluable patients at 12 months.

Table 18. Relation between treatment satisfaction and demographic/clinical parameters and PROs during 12 month observation period (Repeated measures regression models) – Convenience domain

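### The protocol asks how treatment satisfaction relates to illness perception, but no planned analysis relates the TSQM-9 to the B-IPQ.

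*Protocol*

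**What the plan says.** Protocol section 8 states the research question as exploring satisfaction and "how this is related to clinical parameters, quality of life, illness perception and treatment adherence evolution during 12-month follow up". The title-page table and the abstract put the same four items to the reader. Secondary objective #2 covers the relation of satisfaction to demographic and clinical "parameters and PROs during a 12-month observation period".

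Protocol 9.3 lists five questionnaires as patient-reported outcomes: TSQM-9, B-IPQ, MMAS-4, CAT and MMRC. The B-IPQ is named only in the descriptive objective: "To describe patient disease perception (by means of illness perception questionnaire B-IPQ), adherence to COPD treatment (by means of MMAS4".

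For objective #2, protocol 9.7 enters as PRO predictors "level of dyspnea (MMRC score), impact of COPD on a patient's life (CAT) and treatment adherence (MMAS-4 score) collected during observational period". SAP 4.9, Table 17 (reused for Tables 18 and 19) takes MMAS-4 at enrolment and "disease severity in terms of level of dyspnea (mMRC score) or CAT total score (depending on data availability) at enrollment". The reason it gives for taking only one of these two scales is that they are expected to be intercorrelated.

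Awareness is treated differently. Section 8 says: "The patients will be also described as far as health status, presence of dyspnea, exacerbation occurrence, patient disease perception and awareness". It is therefore among the things to be described.

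**The concern.** A study that names a relation in its research question should have at least one analysis that estimates it. Here the instrument is chosen, administered three times and scored (SAP section 3), but the step that connects it to satisfaction is missing. Protocol section 7 itself calls illness beliefs important determinants of adherence, citing a study that used the B-IPQ, and adherence is in the model.

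The omission does not look like a recorded decision. Where SAP 4.9 departs from the protocol on post-baseline covariates, it says so and dates the decision. It gives no reason for leaving out the B-IPQ. The risk is a report that is silent on a stated question, or one that fills the gap with an analysis chosen after the data are seen.

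**Working it through.** **1. The plan's own precision figure.** Protocol Table 2 uses half-width = 1.96 × SD/√N. With SD 21.4 this gives 1.96 × 21.4/√380 = 2.152 and 1.96 × 21.4/√320 = 2.345. With SD 16.6 it gives 1.669 and 1.819. All four match the protocol. They concern the mean global satisfaction score, and the finding does not depend on them.

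**2. The four named relations against the planned analyses.**

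| Relation asked (protocol section 8) | Measure | Analysis with TSQM-9 |
|---|---|---|
| Clinical parameters | Exacerbations, spirometry | SAP Tables 17-19 |
| Quality of life | CAT is the nearest measure | Tables 17-19, if CAT rather than mMRC is kept |
| Illness perception | B-IPQ | None |
| Adherence | MMAS-4 | Tables 17-19 |

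**3. Every SAP analysis that could fill the gap.**
- Tables 10 and 11: TSQM-9 alone.
- Table 12: B-IPQ total and its change, by visit.
- Tables 17-19: age, gender, exacerbations, spirometry, mMRC or CAT, MMAS-4.
- Table 37: TSQM-9 at 12 months against hospitalizations, ER accesses, specialist visits, GP visits, laboratory tests and two therapy counts.
- Tables 45 and 46: TSQM-9 in switchers and non-switchers.

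The SAP's table list runs to Table 46, and none of its titles pairs TSQM-9 with B-IPQ. The count is 0. Of the four PROs in protocol 9.3 other than the outcome, the protocol's model includes three and omits only the B-IPQ.

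**4. What an added correlation could show.** Inputs: N = 320 to 380 (protocol 9.5); the values of r are assumptions. The interval is tanh(atanh(r) ± 1.96/√(N−3)). The detectable r at 80% power, two-sided 5%, is tanh((1.960+0.842)/√(N−3)).

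| Assumed r | 95% CI, N=320 | 95% CI, N=380 |
|---|---|---|
| 0 | −0.110 to 0.110 | −0.101 to 0.101 |
| 0.2 | 0.092 to 0.303 | 0.101 to 0.295 |
| 0.3 | 0.197 to 0.397 | 0.206 to 0.389 |
| Detectable r | 0.156 | 0.143 |

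**5. Cost of incomplete items.** SAP section 3 computes the B-IPQ total only if items 1-8 are all answered. The documents give no missing-item rate. If 1% to 2% of answers were missing independently per item (an assumption), the complete fraction would be 0.99⁸ = 0.923 to 0.98⁸ = 0.851. From 320 patients, about 295 to 272 would remain. At 272 the detectable r is tanh(2.802/√269) = 0.169, so the analysis remains informative. The loss of roughly 8% to 15% is still a reason not to force the B-IPQ into the main model.

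**The case against.** The best defence is that the formal objectives are largely met. The B-IPQ is named only in the descriptive objective, and Table 12 delivers that. Objective #2 says PROs without listing them, the protocol's own covariate list never held the B-IPQ, and SAP 4.9 calls the analysis mainly exploratory. On this view the mismatch is between a narrative sentence and the methods, and rewording the sentence would end it. This limits the seriousness, and it shows that the SAP follows protocol 9.7 here. It does not remove the gap. The sentence appears in three places as the research question, and the B-IPQ is a PRO by the protocol's own list. Rewording would drop the question although the data to answer it are collected.

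Two stronger readings are tempting.

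- **That the awareness score is also missing from a promised relation.** Section 8 does open with "Treatment satisfaction in COPD is associated with disease knowledge", and protocol Table 1 puts the awareness interview under its PRO heading. But that opening sentence is background: section 7 traces it to a survey of how informed respondents felt and how satisfied they were with their physician's management. It is absent from the abstract's statement of the question, and no objective tests it. Awareness is to be described, and SAP Table 16 does so.
- **That the SAP will drop CAT and leave quality of life unanswered.** The SAP gives a collinearity reason for keeping one scale, CAT tolerates two missing items, and both scales are scheduled at every visit. No missing-data figure shows which would be kept.

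A further fair objection concerns the remedy. SAP 4.9 lets the biostatistician remove intercorrelated or sparsely recorded covariates and consider stepwise selection, so a B-IPQ term simply added to the list might not survive. This stands, and the fix allows for it.

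**Conclusion.** The point holds for illness perception. One of the four relations in the research question has no planned analysis, and this follows from reading both documents without any outside figure. A reader might infer that the question can never be answered. The documents do not support that: the B-IPQ is collected at enrolment, 6 and 12 months and scored, so the relation stays estimable once an analysis is written down. The descriptive primary objective is untouched.

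The precision figures assume the protocol's 320 to 380 patients. Tables 17-19 use only patients evaluable at 12 months, which may be fewer.

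A separate, minor point remains on mMRC or CAT. The reason for keeping one is collinearity, but the choice between them is left to data availability, so the report may or may not contain the health-status relation.

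**What to change.** In SAP 4.9, pre-specify for each TSQM-9 domain:

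- **(a)** The correlation with the B-IPQ total score at the same visit, with the type of coefficient named in advance and a 95% confidence interval. Repeat it with the B-IPQ total computed without item 4 (treatment control), because that item overlaps in content with TSQM-9 effectiveness. This gives 3 domains × 3 visits × 2 versions = 18 exploratory coefficients.
- **(b)** One additional run of the Table 17-19 model with the enrolment B-IPQ total forced in. Exempt it from the stepwise, intercorrelation and missing-data exclusion rules. Report it beside the main model, with the number of patients in each.

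Both are needed. Some B-IPQ items (identity, consequences) overlap with CAT and mMRC, so an adjusted coefficient alone may not show the relation that was asked about.

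The cost is SAP wording, three more exploratory model runs, and some patients lost to incomplete B-IPQ items in those runs only. The main models stay as planned. Relating awareness to TSQM-9 is optional.

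For the minor point, fit the model once with mMRC and once with CAT. This avoids entering both together and keeps the health-status relation in the report whichever scale is more complete. It costs three further runs of the main model.

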9. RESEARCH METHODS

9.1 STUDY DESIGN

This is a multi-center, non-interventional (observational) cohort study based mainly on newly collected data.

In 20 Italian Pulmonary Centres about 400 consecutive COPD patients will be enrolled in approximately 8 months (from first patient enrolled). Patients will be followed up for 1 year, with an intermediate evaluation after 6 (+/-1) months from baseline (which is compatible with current clinical practice in Italy for COPD patients management).

No treatment will be administered to the patients on the protocol basis, since this is a non-interventional study and the assessment and treatment of the enrolled patients will be applied according to standard clinical practice. The patients switching or stopping treatment during observation period will not be withdrawn from the study. Few patients are expected to stop treatment during study; if any, for primary objective evaluation they will be censored at the latest available visit.

9.2 SETTING

A log of all patients included into the study (i.e. having given informed consent) will be maintained in the ISF at the investigational site.

Boehringer Ingelheim reserves the right to discontinue the study overall or at a particular study site at any time for the following reasons:

1. Failure to meet expected enrolment goals overall or at a particular study site
2. Any administrative reasons that could significantly affect continuation of the study according to signed site contract
3. Violation of GCP, the CTP, or the contract by a study site or investigator, disturbing the appropriate conduction of the study

The investigator / the study site will be reimbursed for reasonable expenses incurred in case of study termination (except in case of the third reason).

All patients, both female and male gender, referring to pulmonary centers will be consecutively enrolled according to the following criteria:

Inclusion Criteria

7. Patients aged ≥ 40 years
8. Patients must have a documented diagnosis of chronic obstructive pulmonary disease (COPD)
9. Patients with no exacerbations in the last 3 months
10. Patients requiring regular treatment according to GOLD guidelines, i.e.: undergoing stable pharmacological treatment for COPD since at least 3 months
11. Written informed consent to both participation in the study and privacy form
12. Patients capable of discernment and able to read or write in Italian language.

Exclusion Criteria

4. Patients who are currently participating in a clinical trial on experimental drugs.
5. Patients naïve to pharmacological treatment for COPD
6. Diagnosis of Asthma COPD Overlap Syndrome (ACOS)

Study Exit criteria

An individual patient may be withdrawn from the non-interventional study prior to completion if any of the following criteria apply:

4. The patient withdraws consent, without the need to justify the decision.
5. The patient is no longer able to participate (according to clinical judgment)
6. Administrative reasons (inclusion in another clinical trial)

9.3 VARIABLES

This is a non-interventional study and does not impose a therapy protocol, diagnostic/therapeutic procedure, or a visit schedule. Patients will be treated according to the local prescribing information, and routine medical practice in terms of visit frequency and types of assessments performed and only these data will be collected as part of the study.

This is a descriptive study, where patients with COPD, who are on treatment, are enrolled and evaluated during 12-months follow-up.

Exposure is defined as having diagnosis of COPD and being under treatment so in this study all enrolled patients are considered exposed.

The treating physician is asked to complete if possible at every patient visit the appropriate CRF.

Primary endpoint will be the patients' satisfaction to COPD medical treatments evaluated through the TSQM9 at baseline and at follow-up visits.

Secondary endpoints will be: patient disease perception (evaluated by means of illness perception questionnaire B-IPQ), adherence to COPD treatment (evaluated by means of MMAS4), health status (evaluated by means of CAT questionnaire) and dyspnea (evaluated by means of MMRC) during a 12-month observation period. Moreover, socio-demographic variables, smoking habits, medical history at baseline and lung function test results (by means of spirometry), COPD exacerbations, disease severity and medications for COPD, COPD exacerbations and adverse events during follow up will be collected. At each visit, each patient will fill in a structured interview aimed at assess his/her awareness of the disease.

Measurements of parameters will be performed by validated questionnaires or widely accepted instruments (e.g. spirometry).

Pulmonary function tests are a validated and well established measurement tool for lung function testing. Pulmonary function tests will be conducted at clinic visits using the site's

own equipment. FEV1, FVC, and DLCO are standard measurements for the assessment of lung function.

Finally, health care resources related to COPD, COPD exacerbations and adverse events will be evaluated during the observation period.

Table 1 below is the recommended assessment schedule that most likely mirrors the patterns of routine clinical care of most patients.

| Study Visits | Visit 1 | Visit 2 | Visit 3 |
|---|----------|-----------|-------------|
| | Baseline | Follow-up | Follow-up 2 |
| Months | 0 | 6 (+/-1) | 12 (+/- 1) |
| Eligibility criteria Inclusion and exclusion criteria, Informed consent and privacy form | X | | |
| Baseline information (Socio-)demographic variables: age, gender, race, geographic location, housing situation, marital status, educational and employment status | X | | |
| Weight, body mass index | X | X | X |
| Physical examination | X | X | X |
| Life Habits Smoking (yes/no, number of pack/years, smoke duration) | X | X | X |
| Medical History and concomitant diseases. - Charlson Comorbidity Index. | X | X | X |
| COPD medical history: Date of COPD diagnosis (years from diagnosis); n° of COPD exacerbations/year during the previous year to enrolment visit | X | | |
| Functional assessment Lung function test results (FEV1, FVC, FEV1 % of the predicted, RV, TLC,DLCO) according to clinical practice | X | X | X |
| CAT questionnaire | X | X | X |
| COPD Exacerbations** after enrollment Onset and resolution date Severity (mild, moderate, severe) | X | X | X |
| Disease severity (GOLD 2015 Guidelines) | X | X | X |
| Medications related to COPD, COPD exacerbations and adverse events (LABA, LAMA, SABA, SAMA, ICS/LABA, steroids, antibiotics, etc.): drug, dose, frequency, duration of therapy. - Long-Term Oxygen Therapy (liquid and/or concentrate). | X | X | X |
| Change of therapy during observation period and reason for change. | | X | X |
| Non Pharmacological treatment - Pulmonary rehabilitation- | X | X | X |
| Health-care resource consumption related to COPD, COPD | X | X | X |

| Study Visits | Visit 1 | Visit 2 | Visit 3 |
|--|----------|-----------------|-------------------|
| | Baseline | Follow-up | Follow-up 2 |
| Months | 0 | 6 (+/-1) | 12 (+/- 1) |
| exacerbations and adverse events: 
 • Drugs • hospitalization (inward and day hospital) • emergency room access • outpatient visits • GP visits • laboratory tests • clinical examinations | | | |
| Patient Reported Outcomes Questionnaires/scales | | | |
| TSQM-9 | X | X | X |
| MMRC (modified MRC dyspnea scale) | X | X | X |
| CAT | X | X | X |
| MMAS-4 (Morisky Medication-Taking Adherence Scale) | X | X | X |
| Brief Illness Perception Questionnaire | X | X | X |
| Awareness structured interview | X | X | X |
| S(AE) assessment | | X | X |

Table 1. Recorded variables.

*** An exacerbation will be defined as an increase or new onset of more than 1 symptom (cough, sputum, wheezing, dyspnoea or chest tightness) with at least 1 symptom lasting at least 3 days and leading to patient's attending physician to initiate treatment with systemic steroids and/or antibiotics (moderate exacerbation) or hospital admission (severe exacerbation).*

Visit 2 (6+/-1 month), Visit 3 (12+/-1 month) are referred as being the current clinical practice in Italy for COPD patients management.

Data will be collected at inclusion visit, 6 (±1) and 12 (±1) month follow up.

The following questionnaires/scales/patient reported outcomes will be administered to patients. They are briefly described below.

- Treatment Satisfaction Questionnaire, 9 items (TSQM-9);
- Brief Illness Perception Questionnaire (BIPQ);
- Morisky medication Adherence Scale, 4 items (MMAS-4);
- COPD Assessment Test (CAT);
- Modified Medical Research Council Dyspnea Scale (MMRC).

Treatment Satisfaction Questionnaire for Medication, 9 items (TSQM-9)

Patient's self-reported satisfaction or dissatisfaction with pharmacological treatments can be measured using the Treatment Satisfaction Questionnaire for Medication (TSQM) Version 1.4, a validated instrument (45). The TSQM-9 was derived from the original version, and it has a total of 9 items with responses to nearly all items rated on a five-point or seven-point rating scale that provide scores on three scales: effectiveness (3 items), convenience (3

items) and global satisfaction (3 items) (9) . The original version also recorded information about side effects in 5 items (45). However in naturalistic studies, administering the TSQM with the side effects domain could provoke the physician to assess the presence or absence of adverse events in a way that is clinically atypical, carrying the potential to interfere with routine medical care.

The TSQM-9 domain scores (effectiveness, convenience and global satisfaction) will be calculated as recommended by the instrument authors (45,46). The TSQM-9 domain scores range from 0 to 100 with higher scores representing higher satisfaction on that domain.

The questionnaire will be completed by patients at enrolment, 6- and 12-month follow up visits.

Brief Illness Perception Questionnaire

The patient disease perception will be evaluated by the Brief Illness Perception Questionnaire

(Brief IPQ) that is a validated 9-item questionnaire designed to rapidly assess cognitive and emotional representations of illness (ref Broadbent 2006). All of the questionnaire items (except the causal question, item 9) are rated using a 0-to-10 response scale (17). Five of the items assess cognitive illness representations: consequences (Item 1), timeline (Item 2), personal control (Item 3), treatment control (Item 4), and identity (Item 5). Two of the items assess emotional representations: concern (Item 6) and emotions (Item 8). One item assesses illness comprehensibility (Item 7). Assessment of the causal representation is by an opened response item, which asks patients to list the three most important causal factors in their illness (Item 9).

The questionnaire will be completed by patients at enrolment, 6- and 12-month follow up visits.

Morisky medication Adherence Scale 4 items (MMAS-4)

The MMAS-4 is a self-reported, medication-taking behavior scale and consists of four questions about the way patients might experience drug errors or omissions. Each item has a scoring scheme of “Yes” = 0 and “No” = 1. Items are summed to give a non-adherence score ranging from 0 to 4 (42-44); higher score means better adherence to therapy.

The scale will be completed by patients at enrolment, 6- and 12-month follow up visits.

COPD Assessment Test (CAT)

During the 12-month observation period the COPD symptoms will be evaluated by the COPD Assessment Test (CAT). The CAT is an 8-item unidimensional measure of health status impairment in COPD (41). It is designed to measure the impact of COPD on a person's life, and how this changes over time. It contains eight short, simple, patient-completed questions. Patients can choose a score from 0 to 5 for the extent to which the described impairment is true for them, thereby providing a measure of the impact of COPD on their individual health.

The score ranges from 0 to 40; higher scores represent worse health. The CAT score is calculated as the sum of the responded items.

The questionnaire will be completed by patients at enrolment, 6- and 12-month follow up visits.

Modified Medical Research Council (MMRC) dyspnea scale

The modified Medical Research Council (MMRC) dyspnea scale [44] has been in use for many years for grading the effect of breathlessness on daily activities [45, 46]. This scale measures perceived respiratory disability, the WHO definition of disability being “any restriction or lack of ability to perform an activity in the manner or within the range considered normal for a human being”. The MMRC dyspnea scale is simple to administer as it allows the physician to indicate the extent to which the breathlessness affects the mobility of the patient.

The scale will be completed by patients at enrolment, 6- and 12-month follow up visits.

The physician will ask the patient about his/her perceived breathlessness and will use the modified MRC dyspnea scale to classify it into MMRC dyspnea grades [44]:

Grade

- 0 Breathless with strenuous exercise
- 1 Short of breath when hurrying on the level or walking up a slight hill
- 2 Walks slower than people of the same age on the level because of breathlessness or stops for breath when walking at own pace on the level
- 3 Stops for breath after walking about 100 meters or after a few minutes on the level
- 4 Too breathless to leave the house or breathless when dressing or undressing

